8.2. Subject Accountability

The number and percentage of subjects in the full analysis set will be summarized. The number and percentage of subjects who complete the study and of subjects who prematurely discontinue will be summarized. The reasons for premature discontinuation from the study will be summarized as recorded in the electronic case report forms (eCRFs). The study duration will be summarized. A subject disposition listing, including study duration, will be provided for individual subjects.

The glucose-6-phosphatease (G6PC) genotyping results at screening will be listed. For subjects who fail to meet eligibility criteria, the inclusion/exclusion criteria the subjects fail will be listed.

8.3. Protocol Deviations

Major protocol deviations will be summarized for each type. Both major and minor protocol deviations will be listed.

8.4. Investigational Product Administration

8.4.1. Extent of Exposure

The actual dose and volume administered will be summarized and will also be listed. The actual dose will be calculated as dose level (GC/kg) multiplied by screening weight (kg) of the subject.

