## **6.3. Treatment Schedule and Administration**

### **6.3.1. Administration of DTX401**

Subjects will receive a single peripheral IV infusion of DTX401 on Day 1, administered by qualified study personnel, as designated by the Investigator (Table 6). The dose will be determined by the cohort and candidate dose (Section 3.1).

The dose of DTX401 to be administered will be calculated using the subject's weight recorded at Screening. The subject's weight will be verified on Day 0, prior to administration of DTX401, to ensure that their current weight is within 10% of their screening weight (Section 8.2.1). Any subject weighing > 100 kg (> 220 lb) will be dosed as if his or her weight is 100 kg. Prior to infusion, all infusion bag labels will be checked by the study site pharmacist and a minimum of 2 medical personnel charged with administration of DTX401.

The study site must be equipped with emergency resuscitation capabilities. On Day 1, an IV catheter will be inserted into a peripheral vein and flushed with saline.

Detailed instructions for dose preparation and subsequent infusion of DTX401 are provided in the pharmacy manual.

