### **6.3.2. Treatment Compliance**

DTX401 will be administered at the study site via a single IV infusion administered by qualified personnel. The dose, start time, stop time, and volume of infusion will be recorded in the subject's eCRF.

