### **8.2.1. Vital Sign Measurements**

Vital sign measurements will be made at the time points specified in the Schedule of Events ([Table 6](#)). During the study, vital sign measurements are to be collected before any stimulating or anxiety-provoking procedures (eg, phlebotomy). Vital sign measurements will include heart rate, blood pressure (systolic and diastolic), and respiratory rate. Height (at the Screening visit only) and weight will also be recorded.

- On Day 0, weight will be measured to ensure that the weight is within 10% of the screening weight used to calculate the dose of DTX401. Subjects with a confirmed change in weight that is > 10% from Screening should be further evaluated to exclude the presence of an acute condition or illness. If a benign explanation for the weight

change is identified and documented, DTX401 can be given and dosed using the weight obtained on Day 0.

- Vital signs should be measured with the subject having rested for at least 5 minutes beforehand. It is preferred that the measurement be late with the subject rested, rather than on time with the subject not sufficiently rested. If the subject is not sufficiently rested, this needs to be stated in the source documents.
- On Day 1, vital signs will be measured at predose, approximately 5 minutes, and 0.5 ( $\pm$  5 minutes), 1 ( $\pm$  5 minutes), 4 and 8 hours ( $\pm$  15 minutes) after the start of DTX401 infusion. Vital signs will also be measured approximately 22 hours ( $\pm$  1 hour) after the start of infusion, prior to subject discharge.
- It is acceptable for heart rate to be captured from the 12-lead ECG (Section 8.2.3).

Vital sign measurements will be recorded on the appropriate page of the eCRF. The medical monitor should be notified of any clinically significant changes or abnormal value in vital sign measurements (Section 9.1.2). If, in the medical and scientific judgment of the Investigator, a clinically significant change or abnormal vital sign measurement is observed, it should be recorded as an AE or SAE, as defined in Section 9.1.2, on the appropriate pages of the eCRF.

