## **9.2.2. Treatment Noncompliance**

### **9.2.2.1. Overdose Management**

An overdose is any dose of the study product given to or taken by a subject that intentionally or unintentionally exceeds the dose, based on body weight (kg), described in Section 3.1. Overdoses without signs or symptoms do not need to be recorded as AEs; in case of any AEs associated with the overdose, these should be reported in the appropriate AE or SAE page of the eCRF. The actual dose infused will be recorded on the appropriate page of the eCRF.

There is no treatment for overdose. All subjects will be closely monitored at the time of infusion for any adverse effects, and supportive care will be administered at the discretion of the Investigator, as needed, should an overdose be suspected.

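### SAP 8.4.1 labels a planned quantity as the actual dose, and its formula omits the protocol's 100 kg cap and Day 0 weight rule

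*SAP*

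**What the plan says.** SAP 8.4.1 opens by promising an account of what was given: "The actual dose and volume administered will be summarized and will also be listed". It then defines the quantity without qualification: "The actual dose will be calculated as dose level (GC/kg) multiplied by screening weight (kg) of the subject". The change history lists this derivation among the major changes in SAP version 2.0, and SAP section 9 declares no departures from the protocol.

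The protocol sets the dose and records it as follows.

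- **Default weight (Protocol 6.3.1).** The dose is calculated from the "weight recorded at Screening".
- **Cap (Protocol 6.3.1, same paragraph).** "Any subject weighing > 100 kg (> 220 lb) will be dosed as if his or her weight is 100 kg".
- **Day 0 weight (Protocol 8.2.1).** "Subjects with a confirmed change in weight that is > 10% from Screening should be further evaluated". If a benign explanation is found and documented, "DTX401 can be given and dosed using the weight obtained on Day 0".
- **Record of the infusion (Protocol 6.3.2 and 9.2.2.1).** "The dose, start time, stop time, and volume of infusion will be recorded" in the eCRF, and "The actual dose infused will be recorded on the appropriate page of the eCRF".

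**The concern.** The SAP carries over the protocol's default weight rule and drops both exceptions. It also has no term for what was infused, so it returns the same number whether the infusion was complete, cut short or exceeded. The result is a planned dose under the label of an actual one.

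An actual-dose table and listing exist to show where the dose given departed from nominal, and this formula fails in just those cases. The study is first-in-human and dose-finding, with cohorts of 3 subjects and summaries by cohort (SAP 8.1), so one wrong value is a third of a cohort's exposure data. A subject dosed under the cap receives fewer GC per kg of body weight than the nominal level, and the derived figure would hide that.

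**Working it through.** The documents state no total dose in GC, so there is no figure to reproduce. The check compares the two rules directly. **All weights and infused fractions below are assumptions.**

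**Inputs.** D = 2.0 × 10¹² GC/kg (Cohort 1) or 6.0 × 10¹² GC/kg (Cohorts 2 to 4), from Protocol 3.1. The cap is 100 kg (Protocol 6.3.1). The trigger for the Day 0 weight is a change of more than 10% (Protocol 8.2.1).

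**Formulas.**

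- SAP dose = D × W_screen
- Protocol planned dose = D × min(W, 100), where W = W_Day0 if the Day 0 rule was applied and W = W_screen otherwise
- Error = SAP dose / protocol planned dose − 1

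D cancels in the error, so the percentages are the same in every cohort. Results at D = 6.0 × 10¹² GC/kg:

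| Screening weight (kg) | Day 0 weight (kg) | SAP dose (GC) | Protocol planned dose (GC) | Error |
|---|---|---|---|---|
| 70 | 73 | 4.20 × 10¹⁴ | 4.20 × 10¹⁴ | 0% |
| 105 | 105 | 6.30 × 10¹⁴ | 6.00 × 10¹⁴ | +5.0% |
| 110 | 110 | 6.60 × 10¹⁴ | 6.00 × 10¹⁴ | +10.0% |
| 120 | 120 | 7.20 × 10¹⁴ | 6.00 × 10¹⁴ | +20.0% |
| 130 | 130 | 7.80 × 10¹⁴ | 6.00 × 10¹⁴ | +30.0% |
| 70 | 78 | 4.20 × 10¹⁴ | 4.68 × 10¹⁴ | −10.3% |
| 70 | 62 | 4.20 × 10¹⁴ | 3.72 × 10¹⁴ | +12.9% |
| 95 | 106 | 5.70 × 10¹⁴ | 6.00 × 10¹⁴ | −5.0% |

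**Cap.** When W_screen is above 100 kg and is the dosing weight, the error is W_screen/100 − 1. At 120 kg, exposure per kg of body weight is 6.0 × 10¹⁴ / 120 = 5.0 × 10¹² GC/kg, against the nominal 6.0 × 10¹².

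**Day 0 weight.** When both weights are at or below 100 kg, the error is W_screen/W_Day0 − 1. The change must exceed 10%, so the error is beyond 1/1.10 − 1 = −9.1% after a gain, or 1/0.90 − 1 = +11.1% after a loss. A 15% gain gives 1/1.15 − 1 = −13.0%, and a 15% loss gives 1/0.85 − 1 = +17.6%. The last row of the table shows that the two rules can act together and partly offset.

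**Incomplete infusion.** If a fraction f of the planned dose is infused and the weight rules do not apply, the SAP figure overstates the dose by 1/f − 1. That is 11% at f = 0.9, 25% at f = 0.8 and 100% at f = 0.5.

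**The case against.** The strongest reply is that the effect may be nil. No subject weights are given, and for anyone at or below 100 kg whose Day 0 weight is within 10% of Screening the formula equals the protocol's planned dose. The Day 0 route is narrow and permissive. SAP version 2.0 is dated 04 March 2022, and SAP 3.7 reports that the DMC had by then reviewed Week 24 data for Cohort 4, so in this open-label study its authors could have known that nobody was affected.

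Other outputs also give partial cover. Volume administered is summarized and listed in the same section, deviations are listed (SAP 8.3), and weights are listed by subject (SAP 8.4.2 and 8.6.3). The CRM uses fixed nominal doses of 2, 6 and 10 (SAP Appendix 2), so the derivation never enters the MTD estimate. No primary or secondary endpoint uses it, and associations of immune and vector parameters with dose are optional and explored from listings (SAP 8.6.8).

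These points stand as limits on consequence. They do not make the rule correct. Volume does not enter the dose derivation, and a reader who must reconstruct the dose from volume, weight and deviation listings has not been given an actual dose. If no subject was affected, the SAP should still say what it means.

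One practical caution also stands: the protocol does not give the units of the eCRF dose field. If it holds GC/kg rather than total GC, a conversion is still needed.

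**Conclusion.** The derivation is wrong as written. It contradicts the protocol's dosing weight for subjects above 100 kg and, with one trivial exception, for subjects dosed on Day 0 weight. The exception is a screening weight of exactly 100 kg with a Day 0 weight capped back to 100 kg. For every subject it yields a planned quantity labelled as actual.

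Under the assumed weights, the error runs from +5% at 105 kg to +30% at 130 kg. For Day 0 dosing below the cap, it is beyond −9.1% after a gain or +11.1% after a loss. Whether any of the 12 planned subjects falls in these groups cannot be told from the documents. The consequence is limited to the exposure table and listing; dose escalation and the efficacy endpoints are unaffected. It should be corrected.

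**What to change.** Replace the formula in SAP 8.4.1 with three statements.

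1. The actual dose is the dose recorded on the eCRF as infused, in total GC. If the eCRF field holds another unit, the SAP should state the conversion.
2. Actual GC/kg is listed as that dose divided by measured, uncapped body weight, and the SAP names which weight is used. Day 0 weight is the measurement closest to infusion and is collected under Protocol 8.2.1.
3. If a planned dose is also shown, it is labelled as planned and derived as dose level × min(dosing weight, 100 kg). Dosing weight is the Day 0 weight where the more-than-10% rule was applied, and the screening weight otherwise.

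The cost is a short SAP edit and a small programming change. The protocol already has the infused dose, the volume and both weights recorded; the only thing to confirm is the unit of the eCRF dose field. No dosing rule changes.

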8.4.2. Demographic and Baseline Characteristics

Demographic parameters (age; race; ethnicity; sex; weight; height, body mass index [BMI]) will be summarized descriptively and will also be listed by subject.

8.4.3. Medical History and GSDIa Medical History

Medical history will be summarized by body system and will also be listed by subject. GSDIa medical history data will be summarized and will also be listed by subject.

8.4.4. Prior and Concomitant Medication

Both prior and concomitant medications will be coded by drug name and therapeutic class using WHO Drug dictionary. If a subject received a specific medication multiple times or received multiple medications within a specific therapeutic class, that subject will be counted only once for the coded drug name or therapeutic class. Prior and concomitant medications will be summarized in tables and will also be provided in listings.

8.4.5. GSDIa Diet

The prescribed and actual daily GSDIa diet parameters (including total calories, carbohydrates and non-utilizable sugars, protein, and fat) and change from baseline values will be summarized by study visit. Individual subject listing of GSDIa diet data will be provided.

8.5. Efficacy Analysis

8.5.1. Symptom-Free Euglycemia

The time (in minutes) to the first hypoglycemic event (defined as glucose <60 mg/dL [<3.3 mmol/L]) during a controlled fasting challenge at baseline (Day 0), Week 12, 24 and 52, and the change from baseline in time (in minutes) to first hypoglycemic event at Weeks 12, 24, and 52 will be summarized. If the controlled fasting challenge has to be stopped due to symptomatic hypoglycemic event, or the subject is administered intervention (e.g., cornstarch), the time to the first hypoglycemic event will be defined as the time to the controlled fasting challenge is terminated. If there is no hypoglycemic event during the fasting challenge, the time will be censored at the maximum evaluable time (15 hours).

A listing of the controlled fasting challenges and the glucose, lactate, and other local lab parameters (cortisol, free fatty acids, glucagon etc.), and capillary glucose levels (if available) collected during the controlled fasting challenges will be provided. Use of cornstarch and carbohydrates in the dinner prior to controlled fasting challenge and change from baseline will be summarized by visit.

In addition, plots for individual patient profile of controlled fasting challenge hours, plots for individual patient profile of glucose and lactate during controlled fasting challenges will be presented by study visits.

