However, further analysis and review of fasting challenge data after changing the prefasting cornstarch dose to 5g showed significantly lower fasting times in cohorts 2 (W52 and W78) and 3 (W24, W32 and W52). In most instances, low post-prandial levels of blood glucose associates, persistence of high circulating insulin levels, and slow cortisol response to hypoglycemia make it challenging to interpret these results. Available CGM recordings have shown an absence of nocturnal hypoglycemia in these subjects despite an overall reduced frequency and total amount of cornstarch. The reason that several subjects can now sleep through the night at home without experiencing hypoglycemia in the absence of cornstarch consumption, but have shorter time to hypoglycemia during the inpatient fasting challenge is unclear. It could be attributed to the artificial threshold of 60 mg/dL for stopping the fasting challenge. This threshold may not allow adequate glucose release to be induced in subjects with higher insulin and lower cortisol levels. In the home setting, subjects clearly do better as their glucose release seems to be better induced, thereby preventing their glucose levels from falling to dangerous levels.

With Protocol Amendment 6, the dinner meal will be personalized for each subject, and will include a target carbohydrate range and overall composition in protein, fats and dietary fibers that is as close as possible to the subject's most current dinner prescription but not higher than the carbohydrate content of the dinner consumed at their baseline fasting challenge. The prefasting cornstarch dose and time of consumption will be per the respective subject's most recent cornstarch prescription and daily regimen at home. In addition, the threshold for stopping the test was lowered to 54 mg/dL (3.0 mmol/L) or when the subject experiences signs and symptoms of hypoglycemia. The new threshold is justified by the fact that signs and symptoms of hypoglycemia associated with an adrenergic reaction and cerebral glucopenia and most physiological hormonal and metabolic responses responses to hypoglycemia may not occur in GSDIa subjects until they reach these levels of blood glucose values. CGM recording during the fasting test will provide continuous glucose measurement data that will allow Investigators to closely monitor subjects when they reach the lower range of blood glucose (ie, below 60 mg/dL).

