## 2. STUDY OBJECTIVES AND ENDPOINTS

Objective	Endpoint
Primary	
To determine the safety of single IV doses of DTX401 in adults with GSDIa, including the incidence of DLTs.	The incidence of AEs, including the incidence of DLTs at each dose level, TEAEs, and SAEs for each dosing cohort, assessed by severity and relationship to study product.
Secondary	
To establish a dose of DTX401 that achieves symptom-free euglycemia (glucose $\geq$ 54 mg/dL [ $\geq$ 3.0 mmol/L]) in a setting of a controlled fasting challenge to allow further clinical development.	The change from Baseline in time (in minutes) to first hypoglycemic event (defined as glucose $<$ 54 mg/dL [ $<$ 3.0 mmol/L]) during a controlled fasting challenge at 12, 24, and 52 weeks after IV administration of DTX401.
Exploratory	
[REDACTED]	[REDACTED]
[REDACTED]	[REDACTED]
[REDACTED]	[REDACTED]
[REDACTED]	[REDACTED]
[REDACTED]	[REDACTED]
[REDACTED]	[REDACTED]
[REDACTED]	[REDACTED]
[REDACTED]	[REDACTED]

Objective	Endpoint

[REDACTED]
	
 
■ [REDACTED]
 
■ [REDACTED]
 
■ [REDACTED]
 

[REDACTED]
	
 
■ [REDACTED]
 
■ [REDACTED]
 

Abbreviations: AAV8 = adeno-associated virus serotype 8; AE = adverse event; DLT = dose-limiting toxicity; [REDACTED]; G6Pase = glucose-6-phosphatase; GSDIa = glycogen storage disease type Ia; [REDACTED]; IV = intravenous; [REDACTED] SAE = serious adverse event; TEAE = treatment-emergent adverse event.

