### **10.2.3. Efficacy Analyses**

#### **10.2.3.1. Symptom-Free Euglycemia**

The time (in minutes) to the first hypoglycemic event (defined as glucose  $< 54$  mg/dL [ $< 3.0$  mmol/L]) during a controlled fasting challenge will be determined for all subjects at Day 0 and Weeks 12, 24, and 52. Full details of the analysis will be provided in the SAP.

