2.2. Secondary Objective

- To establish a dose of DTX401 that achieves symptom-free euglycemia (glucose ≥54 mg/dL [≥3.0 mmol/L])* in a setting of a controlled fasting challenge to allow further clinical development.
 - * Following protocol amendment 6, the definition of euglycemia for the end of the controlled fasting challenge changed from ≥60 mg/dL (≥3.3 mmol/L) to ≥54 mg/dL (≥3.0 mmol/L)

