4.2. Secondary Endpoint(s)

- The change from baseline in time (in minutes) to first hypoglycemic event (defined as glucose <54 mg/dL [<3.3 mmol/L])* during a controlled fasting challenge at 12, 24, and 52 weeks after IV administration of DTX401.
 - * Following protocol amendment 6, the definition of euglycemia for the end of the controlled fasting challenge changed from \geq 60 mg/dL (\geq 3.3 mmol/L) to \geq 54 mg/dL (\geq 3.0 mmol/L

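### The only secondary endpoint is defined at glucose <54 mg/dL in the protocol but analysed at <60 mg/dL in SAP 8.5.1, and SAP 9 declares no change

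*SAP*

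**What the plan says.** Protocol Section 2 states the secondary endpoint as "The change from Baseline in time (in minutes) to first hypoglycemic event (defined as glucose $<$ 54 mg/dL", with 3.0 mmol/L as the SI value. Protocol 10.2.3.1 repeats that threshold, says the time "during a controlled fasting challenge will be determined for all subjects at Day 0 and Weeks 12, 24, and 52", and leaves the full detail to the SAP.

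The SAP is not of one mind:

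- Section 2.2 takes as its objective a dose that "achieves symptom-free euglycemia (glucose ≥54 mg/dL [≥3.0 mmol/L".
- Section 4.2 defines the endpoint as time to "first hypoglycemic event (defined as glucose <54 mg/dL [<3.3 mmol/L".
- Section 8.5.1, the only place that specifies the analysis, uses "hypoglycemic event (defined as glucose <60 mg/dL [<3.3 mmol/L]) during a controlled fasting challenge at baseline (Day 0" and the later visits.
- Footnotes in 2.2 and 4.2 say "Following protocol amendment 6, the definition of euglycemia for the end of the controlled fasting challenge changed from" 60 to 54 mg/dL. Section 8.5.1 has no footnote and gives no reason for 60.
- Section 9, reserved for departures from the protocol's analyses, records none, although Section 1 lists Amendment 6 among the versions covered.

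Protocol 1.3.1 confirms that challenges before Amendment 6 ended at 60 mg/dL; it speaks of the "artificial threshold of 60 mg/dL for stopping the fasting challenge".

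**The concern.** All of this is current text, not amendment history. A reading of 57 mg/dL satisfies the objective in SAP 2.2 and is an event in SAP 8.5.1. The footnotes disclose that the end-of-challenge level moved, but they do not say how challenges run under the two stop rules are to be analysed together.

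At stake is the meaning of the reported minutes. A challenge that ended at 60 mg/dL normally contains no time to <54. If the protocol's definition were applied to it, the stop time would be a <60 time carrying a <54 label. Where a baseline challenge ran under one stop rule and the follow-up under the other, the change from baseline would then mix two quantities.

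**Working it through.** **1. Units.** The documents' own pairs give the conversion factor: 54/3.0 = 18.0 and 60/3.33 = 18.02; the exact factor is 18.016 mg/dL per mmol/L.

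- 54/18.016 = 3.00 mmol/L
- 60/18.016 = 3.33 mmol/L
- 3.3 × 18.016 = 59.5 mg/dL

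The pair in SAP 8.5.1 (60 with 3.3) is consistent. The pair in SAP 4.2 (54 with 3.3) cannot be reproduced by rounding; its bracket belongs to 60 mg/dL.

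**2. What each stop rule lets one observe.**

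| Challenge | Time to <60 | Time to <54 |
|---|---|---|
| Before Amendment 6 (stop at 60) | observed | not observed, unless a value <54 was recorded |
| Under Amendment 6 (stop at 54) | observed | observed |
| Fast reached 15 hours without an event | censored | censored |

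The table leaves aside challenges ended by symptoms or intervention, which SAP 8.5.1 counts as events at termination.

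**3. How many subjects the earlier stop rule covers.** Protocol 1.3.1 reports that challenges already run when Amendment 6 was written "showed significantly lower fasting times in cohorts 2 (W52 and W78) and 3 (W24, W32 and W52". Protocol 3.1 gives at least 12 weeks between the last dosing in Cohort 1 or 2 and the first dosing in the next cohort.

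- With a Cohort 3 subject at Week 52, every Cohort 2 subject was at Week 52 + 12 = 64 or later (63 allowing the 7-day visit window).
- With a Cohort 2 subject at Week 78, every Cohort 1 subject was at Week 78 + 12 = 90 or later.
- Cohorts 1 and 2 and at least one Cohort 3 subject had therefore passed Week 52: 3 + 3 + 1 = 7 of 12 planned subjects, and up to 9 if all of Cohort 3 had.
- Pairs: 7 × 3 visits = 21 of 12 × 3 = 36, or 58%. The other 36 − 21 = 15 may straddle the amendment or lie wholly on one side, so the number of straddling pairs is between 0 and 15.

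**4. Size of the shift in one challenge.** The documents give no rate of glucose fall, so the rate r is an assumption. Without a sampling grid, the time from 60 to 54 is 6/r × 60 minutes. On the schedule in protocol 8.1.1 (hourly until ≤70 mg/dL, then half-hourly), assume a linear fall with the first hourly value at or below 70 uniform on (70 − r, 70].

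- At r = 30, the first value <60 is also <54 with probability 23/30; otherwise the lag is 30 minutes. Mean = 30 × 7/30 = 7.
- At r = 20, the lag is zero with probability 8/20. Mean = 30 × 12/20 = 18.
- At r = 12, 6 and 3, glucose falls by 6, 3 and 1.5 mg/dL per half-hour, so 1, 2 and 4 further samples are always needed.

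| Assumed fall (mg/dL per hour) | Mean lag, first <60 to first <54 (min) | Zero lag |
|---|---|---|
| 30 | 7 | 77% |
| 20 | 18 | 40% |
| 12 | 30 | 0% |
| 6 | 60 | 0% |
| 3 | 120 | 0% |

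For scale, protocol 1.3.1 allows ±2 hours for variability within a person. The model ignores stops for symptoms. It also ignores the laboratory turnaround of up to 30 minutes, which could let one more sample be drawn before a challenge ended.

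**5. Effect on the endpoint.** The endpoint is a change. With one threshold at both visits, choosing 54 rather than 60 shifts it by the follow-up lag minus the baseline lag, which may partly cancel.

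**The case against.** The best defence is that protocol 10.2.3.1 delegates the detail to the SAP, and SAP 8.5.1 applies one threshold to every visit. That threshold can be read from challenges under either stop rule, so it may well have been chosen on purpose. This stands as a reason for 60. It does not remove the need to say so: SAP 2.2 and 4.2 still point to 54, and SAP 9 says nothing has changed.

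Three stronger readings are tempting, and the documents do not support them.

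- A reader might infer that most earlier stop times would be mislabelled under <54. That depends on the rate of fall. At 30 mg/dL per hour only 23% of challenges would have a stopping value of 54 or above; at 12 or slower, all would. Some, possibly most, is as far as one can go.
- A reader might infer that baseline and follow-up are mixed across stop rules. The documents are equally compatible with Cohorts 1 to 3 wholly before Amendment 6 and Cohort 4 wholly after it, in which case no pair straddles.
- A reader might take the 7 to 120 minutes as bias in the endpoint. They are lags within one challenge, not in the change from baseline.

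It is also fair that the glucose listings and individual profiles planned in SAP 8.5.1 would let a reader re-derive any time that was observed.

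**Conclusion.** The conflict is real and should be corrected before the endpoint is reported. One endpoint carries two thresholds, one unit bracket is wrong, and the SAP does not declare the departure. For at least 7 of 12 planned subjects (21 of 36 pairs) the protocol's <54 time cannot in general be recovered. That count rests on planned enrolment, visits held on schedule, and the cohort spacing stated in the protocol. The size in minutes rests on assumed linear falls and cannot be fixed from the documents.

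The analysis is descriptive, so no error rate or sample size depends on this. Nor would one threshold make all challenges comparable. The prefasting dinner and cornstarch changed after the Cohort 2 Week 12 review and again at Amendment 6, and those differences remain.

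**What to change.** This concerns the analysis definition only, not the rule for stopping a challenge. Reconcile the passages and apply one analysis threshold to all challenges.

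**If <60 mg/dL is kept** (already in SAP 8.5.1 and derivable under both stop rules):

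- state it in SAP 4.2 with the matching bracket;
- record the departure from protocol Sections 2 and 10.2.3.1 in SAP 9;
- explain in SAP 2.2 how a value of 54 to 59 mg/dL relates to the ≥54 objective;
- report time to <54 as supportive for pairs with both challenges under Amendment 6, giving the number of pairs.

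The drawback is that the protocol's own <54 endpoint becomes supportive.

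**If <54 mg/dL is chosen:**

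- correct SAP 8.5.1 and the bracket in 4.2;
- do not enter 60 mg/dL stop times as <54 event times;
- name a method that handles the resulting censoring. The means and standard deviations of change planned in the SAP do not, and where both challenges of a pair are censored the change is not identified.

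In either case, note beside the results that the dinner and cornstarch changes remain. The cost is wording in SAP 2.2, 4.2, 8.5.1 and 9 as the choice requires, plus one small supportive summary (60) or a censored-data method (54). No new data are needed.
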